Behavioral Approaches to Reducing Diabetes Distress and Improving Glycemic Control (EMBARK)

NCT04016558

Study Protocol

8/10/2019

Behavioral Approaches to Reducing Diabetes Distress and Improving Glycemic Control (EMBARK)

Project Summary. Diabetes Distress (DD) is the personal, often hidden side of diabetes: it reflects the unique emotional burdens and strains that individuals with diabetes may experience as they struggle to keep blood glucose levels within range⁷. When high, DD can have a major, negative impact on disease management and glycemic control⁹. High DD is characterized by frustration, feeling overwhelmed, and feeling hopeless and discouraged by the unceasing demands of diabetes. DD is also linked to an individual's beliefs, expectations, current life situation, and personal and social resources¹⁰⁻²⁷.

There have been very few systematic interventions directly aimed at reducing DD among adults with T1D. Furthermore, systematic reviews^{4,5} conclude that, of the few interventions to date, most attempt to reduce DD only indirectly by providing diabetes education and/or enhancing disease management. These interventions, which have yielded only modest improvements in HbA1c, rarely address the powerful and persistent underlying affective experience of DD, and the direct impact of high DD on disease management.

The proposed study is a 3-arm, 12-month RCT to test the added value of a DD-targeted (TunedIn) intervention vs. a unified DD and management intervention (FixIt), relative to a traditional, educational/behavioral-management intervention (StreamLine). Each of the 3 arms will follow a separate, standardized protocol. All participants will receive 3 months of intervention with 9 months of subsequent follow-up (12 months total). We will examine models of disease-management behaviors as mediators of associations between DD and HbA1C, and explore the directions of longitudinal associations among DD, disease management and HbA1c.

Aims & Hypotheses:

Primary Specific Aim 1 Hypothesis 1. Improvement in primary (HbA1C, Diabetes Distress) and secondary (frequency of hypoglycemia, emotion regulation measures) outcomes from baseline to 12-month follow-up will be greater in TunedIn relative to StreamLine, and greater in FixIt relative to either TunedIn or StreamLine.

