Primary Specific Aim 2 Hypothesis 1 (Mediation Hypothesis). Decreases in DD will be significantly associated with decreases in HbA1C within each of the 3 intervention groups over 12 months. Associations between changes in DD and changes in glycemic control will be explained by changes in disease-management mediators (e.g., increased blousing) across all 3 intervention groups. In exploratory analyses, we will examine the direction of associations as presented in the conceptual models in Figure 3.

Secondary Specific Aim 1 Hypothesis 1 (Moderator Hypothesis). Differences in primary and secondary outcomes between FixIt and TunedIn will be qualified by: (a) patient characteristics (with stronger positive effects for younger age and patients with shorter T1D duration), (b) both baseline emotion regulation (ER) skills and level of DD (with stronger positive effects for patients with poorer ER skills and higher DD), and (c) baseline cognitive-processing constructs (with stronger positive effects for patients with lower problem-solving skills and diabetes knowledge).

Secondary Specific Aim 2 Hypothesis 1 (Cost-effectiveness). FixIt and TunedIn will be more cost-effective than StreamLine in terms of improvements in primary and secondary outcomes.

Research Design: This is a 3-arm, 12-month randomized comparison trial (baseline N=118 per arm) to test the added value of a DD-targeted intervention (TunedIn) vs. a unified DD and management intervention (FixIt), relative to a traditional, educational/behavioral-management intervention (StreamLine) to reduce diabetes distress and improve glycemic control in adults with type 1 diabetes. Additionally, the implementation costs and per-participant program costs will be calculated.

Each of the 3 arms will follow a separate, standardized protocol. All participants will receive 3 months of intervention with 9 months of follow-up (12 months total).

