TunedIn (DD-targeted strategy) utilizes exercises and scenarios of ER-based strategies that were effective in reducing DD in the OnTrack arm of T1REDEEM6, now greatly expanded in number and focused in intensity to be more comprehensive and inclusive to help participants observe how what they feel affects what they do regarding disease management. Taking advantage of the power of facilitated group interaction in reducing DD, participants in TunedIn will attend 2 highly interactive group workshops (6 hours followed by 2 hours), facilitated by a psychologist or social worker experienced in diabetes. Each will identify and discuss common emotional responses related to BG management (e.g., over-reacting, avoiding, lack of mindfulness). Between the two workshops (2 weeks), participants will

blood. For those patients who are unable to go to a local laboratory, we will provide a HbA1C home test kit mailed to their home address for their convenience and comfort. After blood sample is provided by patient (instructions are provided in each test kit), they will mail the kit back to the lab to be analyzed. Randomization of eligible participants will occur after baseline assessments. Sequential ID numbers will be generated and randomly assigned to the 3 study groups. Each participant will receive the next ID number, contained in a REDCap database. Block randomization stratified by clinical recruitment site will be used to ensure equivalent distributions in the three intervention study arms across sites. complete a "feeling log," a tool commonly used in ER-based programs, in which participants document.

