FixIt (unified strategy) seamlessly integrates StreamLine and TunedIn. It makes use of the same highly interactive group discussion around affect management using ER techniques and affect logs used in TunedIn with the same 5-point glycemic-management program used in StreamLine. Thus, interconnected feelings and expectations are highlighted as problematic BG patterns are identified. To ensure the delivery of a balanced, integrated approach, FixIt will be co-facilitated by a psychologist/social worker experienced in diabetes (as in FixIt) and a CDE (as in StreamLine). Participants will attend 2 group workshops (6 hours followed by 4 hours), separated by 2 weeks. Between the 2 workshops, participants will record their BG data for 3 days and keep a parallel “affect log” to provide context. They will then meet face to face or through phone/video for 30 minutes with one of their 2 group interventionists to review the collected data and begin the process of identifying a specific glycemic problem, along with an action plan to address it. Full discussion of DD-related aspects of the plan will also be included to both enhance mindfulness and identify typical ER strategies that may reduce DD and ease problem resolution. At the second group session, these plans will be shared to shape the plan to make it more personally actionable. Participants will be further supported by: 3 online video group meetings (60 minutes, monthly) utilizing facilitated group discussion to review specific plans addressing behavioral and affective management for each participant, and 3 additional individual participant/facilitator meetings (face to face or phone/video, 30 minutes) to review BG data and the contextual and DD barriers to change. This strategy, therefore, combines the primary intervention modalities of StreamLine and TunedIn.

Measures

Telephone screening questions will document: age, years with T1D, age at diagnosis, insulin treatment (multiple-dose injection [MDI], CGM, insulin pump), co-morbidities and diabetes-related complications, and English language skills (attached). Self-reported surveys completed electronically will include the following measures:

- The **number of hypoglycemic episodes** will be assessed, including: frequency of symptomatic hypoglycemia (BG < 70 Mg/dL) in the past week and episodes of hypoglycemia in the past 6 months (or since last follow-up) requiring the assistance of another person or medication intervention (2 items)⁸².

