Data Analysis. Descriptive statistics will be computed for baseline characteristics, initially testing for differences between: (1) intervention arms and (2) patient dropouts vs. non-dropouts. Patient-level demographic and disease status covariates will be screened in bivariate analyses and included in multivariate analysis if they are related to the outcome at $p < .20$, significantly differ between treatment arms, or are associated with dropout. Correlations among variables within each area of secondary outcomes and moderators (see measures above) will be examined, and redundant measures will be combined or eliminated to avoid multicollinearity. In the event normality assumptions are not met, we will use transformations to normalize distributions, ordinal or Poisson regression where appropriate, and/or the appropriate link function (e.g., logit link for dichotomized measures)⁹⁵⁻⁹⁷. We will examine change in outcomes across groups will be evaluated by ANCOVA. In these models, the follow-up value is specified as the outcome, the baseline value as the covariate, and treatment group was a fixed effect. When the treatment group effect was statistically significant ($p < 0.05$), Helmert contrasts will be used to determine differences among the three groups. Missing values will be imputed with NORM software (version 2.0; The Methodology Center, Penn State, University Park, PA) (23,24) using multiple-imputation procedures to create a stable, complete data set. Parallel analyses will be performed with raw and imputed data sets. Hypothesis tests will be 2-sided with alpha set at .05. Goodness-of-fit tests and model-fitting diagnostics will be used to assess for influential points, outliers, over-dispersion, and heteroscedasticity, and to evaluate alternative model specifications.¹⁴³

Intervention implementation costs on a per-participant basis, and training costs on a per-facilitator basis, will be calculated using activity-based costing methods. Costs for staff time will be assigned based on the prevailing national wage rate as reported in the Bureau of Labor Statistics' Occupational Outlook Handbook in the final year of intervention implementation⁹². All other costs will be adjusted for inflation

to constant U.S. dollars for the final year of implementation using the Bureau of Labor Statistics'

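### The plan states a cost-effectiveness hypothesis but only calculates costs, and it never assesses what FixIt adds over TunedIn for any extra cost

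*Combined protocol and SAP*

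**What the plan says.** The hypothesis under Secondary Specific Aim 2 is "FixIt and TunedIn will be more cost-effective than StreamLine in terms of improvements in primary and secondary outcomes". StreamLine is the only comparator it names.

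The Research Design section promises costs and nothing further: "Additionally, the implementation costs and per-participant program costs will be calculated". Data Analysis gives the method: "Intervention implementation costs on a per-participant basis, and training costs on a per-facilitator basis, will be calculated using activity-based costing methods". It then sets staff wage rates and an inflation adjustment. The last costing sentence breaks off at the end of Data Analysis, and its ending, the name of the price index, appears inside the Consent process text. What follows it there is about consent, not about an economic analysis.

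Elsewhere FixIt is compared with both other arms. Aim 1 expects improvement to be "greater in FixIt relative to either TunedIn or StreamLine", and the description of FixIt closes with "This strategy, therefore, combines the primary intervention modalities of StreamLine and TunedIn".

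**The concern.** There are two gaps.

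- **No analysis for the hypothesis.** To call one arm more cost-effective than another, costs and effects must be brought together. The plan names no incremental ratio or net benefit, no outcome for the denominator, no perspective, no dominance rule and no measure of uncertainty. Carried out as written, it ends with a cost per arm.
- **The comparator leaves out a key increment.** The three programs are alternatives, and FixIt is built from the other two. Whether FixIt is worth choosing turns on what it adds over the next cheaper effective program, which may be TunedIn. A ratio of FixIt to StreamLine credits FixIt with whatever benefit TunedIn would already have delivered.

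If the method is left open until results are known, both the comparator and the outcome can be chosen after the fact.

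**Working it through.** **The plan's own figures.** The documents state no cost and no cost-effectiveness figure, so there is none to reproduce. The sample-size paragraph is used here only for a standard deviation (SD). It gives 90 per group, d = 0.47, and detectable changes of 0.44 HbA1c points and 0.36 T1DDS points. Power is not stated; a two-sided t test at 0.05 with these inputs has 88%.

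**Staff time that can be read.** For TunedIn, "participants in TunedIn will attend 2 highly interactive group workshops (6 hours followed by 2 hours", led by a psychologist or social worker (one facilitator assumed). For FixIt, "Participants will attend 2 group workshops (6 hours followed by 4 hours), separated by 2 weeks", co-led by two facilitators.

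- TunedIn workshops: (6 + 2) × 1 = 8 facilitator-hours per group.
- FixIt workshops: (6 + 4) × 2 = 20 facilitator-hours per group, or 20/8 = 2.5 times as much.
- Per participant, with the stated 8 to 10 per group: 0.8 to 1.0 h against 2.0 to 2.5 h.

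The rest of the TunedIn schedule is broken in the extracted text, so its total contact time cannot be compared with the other arms. Hours are also not costs, because the arms use different professions at different wage rates.

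**How far the choice of comparator matters (illustration on assumed costs and effects).** Let TunedIn cost 1 unit more than StreamLine and gain 0.44 HbA1c points over it. Let FixIt cost *k* units more than StreamLine, with *k* from 1.25 to 3, and gain *e* points over TunedIn.

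- FixIt v StreamLine = *k* / (0.44 + *e*)
- FixIt v TunedIn = (*k* − 1) / *e*

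| *e* (points) | FixIt v StreamLine (units per point) | FixIt v TunedIn (units per point) | Multiple |
|---|---|---|---|
| 0.02 | 1.25/0.46 = 2.7 to 3/0.46 = 6.5 | 0.25/0.02 = 12.5 to 2/0.02 = 100 | 4.6 to 15 |
| 0.10 | 1.25/0.54 = 2.3 to 3/0.54 = 5.6 | 0.25/0.10 = 2.5 to 2/0.10 = 20 | 1.1 to 3.6 |
| 0.44 | 1.25/0.88 = 1.4 to 3/0.88 = 3.4 | 0.25/0.44 = 0.57 to 2/0.44 = 4.5 | 0.4 to 1.3 |

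As *e* approaches zero, the first ratio stays finite and the second grows without limit. When *e* is as large as TunedIn's own gain, the two ratios are of similar size.

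**Precision of the denominator.** The implied SD for HbA1c change is 0.44/0.47 = 0.94. The standard error of a difference between two arms of 90 is 0.94 × √(2/90) = 0.14, so the 95% half-width is 1.973 × 0.14 = 0.28 points. A true FixIt–TunedIn difference of a few hundredths could not be told from zero, and a bare ratio would be unstable.

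**The case against.** The strongest reply is that nothing is hidden. Aim 1 already compares FixIt with TunedIn on effects, and per-participant costs will be calculated for every arm, so a small gain at a higher cost could be seen from planned output. StreamLine is also a reasonable reference, being the traditional program. This stands in part: the data needed are planned. But the comparison itself is not, and Aim 1 does not fully fill the gap. Data Analysis says that "Helmert contrasts will be used to determine differences among the three groups", only after a significant overall test and without giving the order of the arms. Under some orders (FixIt against the mean of the other two, then TunedIn against StreamLine), FixIt versus TunedIn is not one of the contrasts.

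A reader might go further and infer that FixIt will be declared cost-effective while its extra cost over TunedIn buys almost nothing. The documents do not support that. They give no costs and no expected FixIt–TunedIn difference; 0.44 appears only as a detectable change, and Aim 1 predicts that FixIt does better. It is not even known whether TunedIn costs more than StreamLine.

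A reader might also infer that costing training per facilitator leaves it out of the comparison and so flatters FixIt, which uses two disciplines. The text does not say that training is excluded. It is silent on how that cost reaches the per-participant figure, and it does not give the number of participants per trained facilitator.

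**Conclusion.** The concern holds in this form: a stated secondary hypothesis has no analysis that can support or refute it, and FixIt is never compared with TunedIn on cost-effectiveness. That follows from the text alone and needs no assumption.

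The size of any distortion is unknown. Under the assumed costs, the multiple runs from 0.4 to about 15 as FixIt's gain over TunedIn falls from 0.44 to 0.02 points; it could be large if FixIt adds little and small if it adds much. The only supported cost signal between these two arms is workshop staff time, 20 against 8 facilitator-hours per group, on the assumption of one TunedIn facilitator.

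The aim is secondary and the sample size is unaffected, so this should be corrected but does not threaten the primary comparison.

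**What to change.** Revise the Secondary Specific Aim 2 hypothesis and the costing paragraph of Data Analysis to prespecify a full incremental analysis of all three arms:

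- Run it separately for 12-month HbA1c and for T1DDS, and state the perspective and the time horizon.
- Order the arms by mean cost per participant, with training cost allocated to participants under a stated rule.
- Apply dominance separately within each outcome, since an arm may be dominated on one and not on the other.
- Report incremental cost and incremental effect against the next non-dominated arm, and always report FixIt versus TunedIn, whatever the ordering.
- Show bootstrap uncertainty as joint cost–effect intervals or acceptability curves, not as a ratio alone, because the effect difference may be near zero.

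The cost is revised wording and a little more computation on costs and outcomes already planned for all three arms. The downside is that the FixIt result may look less favorable.

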Sample size and power estimates are based on two-sided $\alpha = 0.05$ and Student t tests on change from baseline to each follow-up point. Estimating a 20% attrition rate, a sample of 90 per group allows for detection of moderate effect sizes ($d = 0.47$ SD unit differences) equating to mean changes in DD of at least 0.36 and mean changes in HbA1c of at least 0.44%.

Inclusion criteria:

To be eligible to enter baseline assessment:

- Adult patients with T1D (confirmed by clinical history and/or anti-glutamic acid decarboxylase [GAD] antibody testing) on intensive insulin treatment;
- Diagnosis of T1D for at least 12 months that occurred at or below age 40;
- Age 19 years or older;
- Have a recent HbA1c of 7.2% or higher, or unable to recall most recent value;
- Not have started to use any new (to the participant) diabetes device (such as an insulin pump or continuous glucose monitor) in the past 6 months;
- Internet access through a computer or smart phone;
- Ability to speak/read English.

To be eligible to be randomized to receive an intervention (following baseline assessment):

- Type 1 Diabetes Distress Scale (T1DDS) mean score 2.0 or higher;
- HbA1c 7.5 or higher.

Exclusion criteria:

- Documented psychosis, blindness, dementia, active dialysis, substance abuse, amputations, or severe functional deficits, or recent major surgery or hospitalization in the past year.

Consent process

During the telephone screening call, patients will be invited to give verbal consent to be screened for eligibility. Verbal consent will be documented by the researcher. Following determination of eligibility and interest, the study protocol will then be described to individuals. During the initial recruitment conversation, potential participants will be asked open-ended questions and they will be invited to repeat back their understanding of the study. Individuals will then be asked to report their name, mailing address, phone number, and email address.

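### Randomisation is stratified by recruitment site, but site is not pre-specified in the ANCOVA (minor; a cheap improvement)

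*Combined protocol and SAP*

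**What the plan says.** The randomisation text (in the extracted file it falls inside the description of TunedIn) reads: "Block randomization stratified by clinical recruitment site will be used to ensure equivalent distributions in the three intervention study arms across sites".

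Data Analysis specifies an ANCOVA of the follow-up value, with "the baseline value as the covariate, and treatment group was a fixed effect". If the group effect is significant, "Helmert contrasts will be used to determine differences among the three groups". Two further statements bear on the point:

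- Other covariates can enter: "Patient-level demographic and disease status covariates will be screened in bivariate analyses". They are kept if related to the outcome at p < .20, if they differ between arms, or if they are associated with dropout. Site is not named.
- On missing data, "Parallel analyses will be performed with raw and imputed data sets". The variables in the imputation model are not listed.

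The sample size paragraph is based on "Student t tests on change from baseline to each follow-up point" and does not mention site. It says: "Estimating a 20% attrition rate, a sample of 90 per group allows for detection of moderate effect sizes". Research Design gives "baseline N=118 per arm".

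**The concern.** Blocking within site balances site differences across arms, so they largely drop out of the true sampling variance of a treatment comparison. A model without site still counts them as residual error. The model-based standard error is then larger than the true one, and the precision that the stratification could provide is not used.

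At stake are slightly wide confidence intervals, tests that run below their nominal level, and a small loss of power. If the choice stays open, whether to adjust for site could also be decided after outcomes have been seen.

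**Working it through.** **The plan's own figure.** With d = 0.47, two-sided α = 0.05 and 80% power (assumed, as none is stated), n = 2(1.960 + 0.842)²/0.47² = 71.1, so 72 per arm, and 72/(1 − 0.20) = 90. The stated 90 is therefore reproduced as a number before attrition. It can also be read as 90 evaluable, which gives 88.4% power by the normal approximation. Neither reading matches 118 per arm exactly (118 × 0.8 = 94.4; 90/0.8 = 112.5, so 113). That is a separate matter, and both 90 and 72 are carried below.

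**Assumption.** Let r be the share of the residual variance, after baseline adjustment, that lies between sites. The documents do not give r, the number of sites or the block size. I use r = 0, 2, 5 and 10%.

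**Width and size (normal approximation).**

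- CI excess = 1/√(1 − r) − 1.
- α for a single contrast = 2[1 − Φ(1.96/√(1 − r))].
- Omnibus α (2 df) = P(χ² > 5.99/(1 − r)).

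| r | CI too wide by | pairwise α | omnibus α |
|---|---|---|---|
| 0 | 0% | 5.0% | 5.0% |
| 2% | 1.0% | 4.8% | 4.7% |
| 5% | 2.6% | 4.4% | 4.3% |
| 10% | 5.4% | 3.9% | 3.6% |

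The first two formulas do not depend on the contrast coefficients, so they apply to each Helmert contrast as well.

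**Pairwise power, d = 0.47 in residual SD units.** With δ = 0.47/√(2/n), δ = 3.153 at n = 90 and 2.820 at n = 72.

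- Without site: Φ[(δ − 1.96)/√(1 − r)].
- With site: Φ[δ/√(1 − r) − 1.96].

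| r | n = 90, without / with | loss (points) | n = 72, without / with | loss (points) |
|---|---|---|---|---|
| 2% | 88.59 / 88.97% | 0.4 | 80.75 / 81.29% | 0.5 |
| 5% | 88.95 / 89.88% | 0.9 | 81.12 / 82.47% | 1.3 |
| 10% | 89.57 / 91.36% | 1.8 | 81.77 / 84.44% | 2.7 |

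Losses are taken before rounding. At r = 0 the loss is 0.

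**Omnibus power.** Assume equally spaced arm means of 0, 0.235 and 0.47. The noncentrality is n × 2 × 0.235²/(1 − r), with numerator 9.94 at n = 90 and 7.95 at n = 72. The critical value is 5.99 with site and 5.99/(1 − r) without. For r = 2, 5 and 10% the loss is 0.7, 1.7 and 3.4 points at n = 90, and 0.9, 2.2 and 4.5 at n = 72.

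**Change scale.** The plan's d is on change from baseline. With equal variances, ANCOVA residual variance is (1 + ρ)/2 of change variance, so 0.47 becomes 0.543 at ρ = 0.5 and 0.510 at ρ = 0.7 (both ρ assumed). At n = 90 the pairwise loss is then 0.2–0.3, 0.4–0.6 and 0.8–1.2 points, and the omnibus loss 0.4–0.5, 1.0–1.3 and 1.8–2.5.

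**Simulation check on the omnibus test.** Assumed: 6 sites, blocks of 6, 90 per arm, 4,000 trials (Monte Carlo SE about 0.3 points). Size without / with site was 5.8/5.9% at r = 0, 5.0/5.6% at 5% and 3.4/4.9% at 10%. The direction agrees.

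**Workshop groups.** Assume 7 completers per group and an intragroup correlation (ICC) of 0.02 of total residual variance, equal in all arms, with r = 5%. The true variance factor is 0.95 + 6 × 0.02 = 1.07.

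- Without site: α = 2[1 − Φ(1.96√(1/1.07))] = 0.058.
- With site: α = 2[1 − Φ(1.96√(0.95/1.07))] = 0.065.

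An ICC of 0.05/6, about 0.008, already cancels the conservatism at r = 5%.

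**The case against.** The case against is fourfold.

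1. **The consequence is very small.** Site is a recruitment source that contacts its members by e-mail or social media (Recruitment), and participants choose their own laboratory (Laboratory Assessments). Both point to a low site share, and the 5% and 10% shares have no source in the documents. This stands, and it is why the point is minor.

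2. **The model is not closed.** A reader might infer that the analysis can contain only the baseline value and arm, or that site is barred. The documents do not support that: screened covariates may enter, and the section allows alternative model specifications to be evaluated. What can be said is that site is not pre-specified. The screen is not a substitute. Site is neither a demographic nor a disease status variable, and stratification makes a between-arm difference in site unlikely.

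3. **The 90-evaluable figures are not a ceiling.** A reader might take a loss of 0.4 to 1.8 points as the upper bound. It holds only for pairwise tests with 90 evaluable per arm; 72 evaluable, or the omnibus test, gives more.

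4. **Adding site alone can worsen error control.** This stands in part. The Interventions section describes workshops of 8–10 participants. If outcomes correlate within groups and the model ignores it, a site term moves α further above 5%. An unknown, accidental offset is not a reason to leave site out, but the downside has to be stated with the recommendation.

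**Conclusion.** The point holds as a minor one: the stratification factor is not pre-specified in the analysis. A reader might infer bias, inflated false positives or an invalid sample size. None follows, since omitting a balanced factor does not bias the comparison and, for site alone, errs on the conservative side. Nor can the trial's tests be called conservative overall, because group clustering acts in the opposite direction and its size is not given.

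The size rests on the assumed site share, on whether 90 is counted before or after attrition, on the scale of d and, for the omnibus test, on equally spaced arms. Across the shares examined, the largest loss is 4.5 points of omnibus power (10% share, 72 evaluable). If site explains nothing, nothing is lost.

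**What to change.** Add to Data Analysis:

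> The model for each outcome, and the Helmert contrasts derived from it, will include recruitment site as used in randomisation, regardless of the p < .20 screen. This applies to the raw and the imputed analyses, and site will be included in the imputation model. Small sites will be pooled, or site fitted as a random intercept, by a rule set before outcome data are seen.

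In the same model, specify how correlation within workshop groups is handled, so that the site term does not simply remove a partial offset to it.

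For site, the cost is wording only, since it is already recorded for randomisation; handling groups also requires group membership in the analysis file. In simulations with assumed site structures where site explained nothing, fixed effects for 3–10 sites changed pairwise power by −0.2 to +0.1 points, within Monte Carlo error. With 30 sites of 4–44 participants, fixed effects cost 2.0 points of omnibus power (SE 0.3) and pooling sites under 15 cost 0.5 (SE 0.2), while a random intercept changed it by +0.2 (SE 0.1). That is the reason for the small-site rule. The cut-off of 15 is only an example.

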- The **Type 1 Diabetes Distress Scale (T1DDS)**, an internally reliable, validated 28-item scale (alpha=.84)²⁸ will be used to assess total DD plus 7 DD subscales: management, powerlessness, hypoglycemia, eating, friends/family, physician, and negative social perceptions.
- Depression symptoms will be assessed using the 8-item **Patient Health Questionnaire depression screener (PHQ-8)**^{74,75}
- The personal control subscale from the **Revised Illness Perception Questionnaire** (6 items; alpha=.80)⁸⁷ will assess participants' perceived control over their illness.
- The **Five Facet Mindfulness Questionnaire**⁸⁸, a validated and widely used measure based on a factor analytic study of 5 independently developed mindfulness measures, will be used to assess: **non-judging of experience, and nonreactivity to inner experience**.
- We also will include the only validated diabetes-specific ER scales to assess self-compassion in the context of diabetes management (SCS-D, 19 items; alpha=.9490). Diabetes-specific self-compassion will be measured using the **Self-Compassion Scale - Diabetes (SCS-D)** (19 items; alpha=.94)⁹⁰.
- **Missed insulin boluses** will be measured using self-reported numeric report of missed insulin boluses over a 7 day period.

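### The combine-or-eliminate rule for multicollinearity should not apply to secondary outcomes: each is modelled on its own, so dropping or merging one gains nothing, and the rule sets no timing

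*Combined protocol and SAP*

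**What the plan says.** The Data Analysis section sets out a data-reduction step that comes before the outcome models: "Correlations among variables within each area of secondary outcomes and moderators (see measures above) will be examined", after which "redundant measures will be combined or eliminated to avoid multicollinearity". Secondary outcomes and moderators fall under the same rule.

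The outcomes concerned are named in Aims & Hypotheses, Primary Specific Aim 1 Hypothesis 1, as "secondary (frequency of hypoglycemia, emotion regulation measures) outcomes from baseline to 12-month follow-up". The Measures section lists the instruments. Those that fit the emotion regulation label are two facets of a mindfulness questionnaire, "non-judging of experience, and nonreactivity to inner experience", and a diabetes self-compassion scale introduced as one of "the only validated diabetes-specific ER scales to assess self-compassion in the context of diabetes management". Hypoglycemia has two items: "frequency of symptomatic hypoglycemia (BG < 70 Mg/dL) in the past week and episodes of hypoglycemia in the past 6 months" requiring help from another person or medication.

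The same Data Analysis paragraph defines the outcome model. It is an ANCOVA with the follow-up value as outcome, that outcome's baseline value as covariate and treatment group as fixed effect, tested two-sided at .05.

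**The concern.** Multicollinearity arises among predictors in one regression: correlated predictors inflate the standard errors of each other's coefficients. Secondary outcomes analysed one at a time are not predictors of one another, so their mutual correlation cannot do this. For outcomes, the rule removes or merges measures to solve a problem that the stated model does not have.

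The rule is also open. It gives no correlation cut-off, no rule for which measure is kept, no method for forming a composite and no commitment to report what was dropped. It does not say whether baseline or follow-up data are used, or when the step occurs relative to seeing results by arm. At stake is whether the secondary part of Aim 1 Hypothesis 1 is tested on a set of outcomes fixed in advance.

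**Working it through.** The plan gives no figure for this rule, so there is none to reproduce. The check has three steps.

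**Inputs from the documents.** Three arms; 90 per group (sample-size paragraph); ANCOVA with own baseline and group; alpha .05 two-sided, with an overall test of group coming first (Data Analysis); two mindfulness facets and one self-compassion scale (Measures).

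**Inputs assumed.** Correlation *r* between measures (the documents give none): 0.7 to 0.9 for measures that might be called redundant. Correlation between baseline and follow-up: 0.6. No true effect on any measure.

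**Step 1. Does correlation between outcomes harm the model?** With unit variance, the standard error of a difference between two arms in the stated ANCOVA is approximately

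SE = √(1 − 0.6²) × √(2/90) = 0.8 × 0.149 = 0.119.

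The correlation between different outcomes does not appear in this formula. Simulation agrees: the SE stayed at 0.119 to 0.120 as that correlation went from 0 to 0.9. Dropping or merging outcomes therefore cures no collinearity.

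**Step 2. What if measures are reduced by correlation, as the rule says?** In null simulations (6,000 runs, *r* = 0.7 and 0.9, two to four measures), keeping the measure with the highest pooled follow-up correlation gave 4.7% to 5.3% false positives. Averaging the measures gave 5.0% to 5.4%. Neither inflates the error rate, even when follow-up data are used, provided the choice ignores the treatment effect.

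**Step 3. What is the worst case that the wording leaves open?** Suppose the measure kept is the one with the smallest p-value. Its false-positive rate is P(min p < .05). For independent measures this is 1 − 0.95² = 9.8% for two and 1 − 0.95³ = 14.3% for three. Correlation lowers it:

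| Measures | r = 0.7 | r = 0.9 |
|---|---|---|
| 2 | 8.4% to 8.5% | 7.3% |
| 3 | 10.8% to 12.1% | 8.4% to 8.9% |

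The ranges come from separate simulations of 4,000 to 20,000 runs. The 20,000-run value for three measures at *r* = 0.7 is 11.3%, with simulation error √(0.113 × 0.887 / 20,000) = 0.2 percentage points. The 12.1% comes from 4,000 runs, with error √(0.121 × 0.879 / 4,000) = 0.5 points, and is compatible with it. In round figures, the worst case is about 8% for two measures and 9% to 11% for three.

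**The case against.** The strongest defence is that this is ordinary preparatory data reduction. The sentence sits among preliminary steps, after baseline descriptives and covariate screening and before the ANCOVA. Its criterion is correlation between measures, not treatment effect. Merging redundant scales under a fixed rule can also reduce the number of tests. All of this stands, and step 2 supports it. For moderators the rule is legitimate: Secondary Specific Aim 1 uses baseline emotion regulation and diabetes distress together, and collinearity can matter there. It does not follow that the rule is right for outcomes. The reason given is collinearity, not multiplicity, and a rule meant to limit multiplicity would need its composite fixed in advance.

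A second objection also stands. P(min p < .05) is equally the chance of at least one false positive when all the measures are tested separately at .05. Reporting every outcome does not lower that chance. The gain is that the reader sees all the results, and not one whose selection is hidden.

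A reader might infer three stronger points that the documents do not support:

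- **That outcomes will be selected by their results.** Nothing in the plan provides for this; the plan merely fails to exclude it.
- **That four emotion regulation measures are at risk, with a worst case of 13.4% at *r* = 0.7.** This requires counting the personal control subscale, which Measures describes as perceived control over illness and does not label as emotion regulation.
- **That a dropped outcome could not be detected.** The public protocol lists the instruments, so an absent scale can be noticed by comparison, though a reader could not learn why or when it was dropped.

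**Conclusion.** The concern holds in a limited form. The stated reason cannot justify dropping or merging secondary outcomes under the plan's own ANCOVA, and the rule does not bar doing so after follow-up results are known. This conclusion rests on the text and needs no assumed figure.

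The inflation is a worst case and not an expected value. It applies only if the retained measure is picked by its result, and it depends on the assumed correlation and on how many measures are treated as redundant. Reading the two mindfulness facets as emotion regulation measures is an inference from Measures, since Aim 1 Hypothesis 1 does not name the instruments. HbA1c and diabetes distress, the primary outcomes, lie outside the rule, and the plan claims no family-wise error control for secondary outcomes that could be breached. The change is still worth making, because it corrects a stated rule at almost no cost.

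**What to change.** In Data Analysis:

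1. Limit the combine-or-eliminate sentence to moderators and covariates entered jointly in one model.
2. Name the instrument behind each secondary outcome in Aim 1 Hypothesis 1, and state that every one is analysed and reported in its original scoring.
3. If a composite is wanted, fix its components and scoring from baseline data, or from pooled data blind to arm, before any follow-up result by arm is seen.

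The cost is a wording change, no new data and a few more secondary results to report. The downside is that the chance of at least one false positive across those tests is not reduced. The plan should therefore say either that they are interpreted as secondary findings or that a multiplicity adjustment is applied across them.
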